## 8.2 Laboratory Evaluations

- **Comprehensive Metabolic Panel (CMP)** – Blood test to assess levels of electrolytes, how well the kidneys and liver are working, and blood glucose. Includes 14 blood tests that provide information about the current health status of the patient. Performed at baseline to assess whether the subject is healthy enough to participate in the study. Performed at intervals during the study to confirm no change in subject’s health. Vitamin B12 and TSH will also be assessed.
- **ApoE** – Polymorphism of the apolipoprotein (ApoE) gene and its effect in modulating hippocampal change will be assessed.
- **Lipid Panel** – Provide a profile of cholesterol, HDL, LDL, and triglycerides to assess cardiac risk and general health of the subject
- **Complete blood count (CBC)** – Gives information about the cells in a patient’s blood, including hemoglobin, hematocrit, and white blood cells to assess patient’s general health.
- **C-reactive protein (CRP) and Lp-PLA2 and MPOS** – Blood markers for inflammation in the body. These inflammatory markers are implicated in the pathogenesis of AD and VD. CRP is a strong marker of vascular disease in early stages of the disease.
- **Blood viscosity** – AD patients have significantly increased whole blood viscosity which is correlated with disease severity.

---

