#### Confidentiality Statement

---

The confidential information in this document is provided to you as an investigator or consultant for review by you, your staff, and the applicable Institutional Review Board. Your acceptance of this document constitutes agreement that you will not disclose the information contained herein to others without written authorization from the sponsor.

The secondary effectiveness endpoints of the study include:

- The safety of Renew™ NCP-5 treatments as reflected in adverse events, labs and vital signs;
- The average of the change from baseline in Alzheimer’s Disease Cooperative Study-Activities of Daily Living (**ADCS-ADL**) Total Score at 12, 18 and 24 weeks after initiation of treatment;
- The answers to the NIA’s Disease Cooperative Study-Clinical Global Impression of Change Scale (**ADCS-CGIC**) at 12, 18 and 24 weeks after initiation of treatment;
- The average of the change from baseline in executive function, assessed by the **Trail Making Test B** at 12, 18 and 24 weeks after initiation of treatment;
- The average of the change from baseline in **ADAS-Cog14** at 12, 18 and 24 weeks after initiation of treatment. ADAS-Cog14 score will be calculated using the subtests from the vADAS-Cog test and will not be conducted as a separate test.

Sponsor will repeat the analysis and conduct the battery of secondary endpoints on the 9 and 12 month data.

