## 8.4 Study Visits

### 8.4.1 Screening (-35 to -7 days prior to baseline)

Screening assessments ascertain whether the patient is eligible to participate in the study. Assessments that require the least imposition on the patient and the staff will be performed first to exclude patients before they are subjected to more demanding assessments. As necessary, screening may be performed on multiple visits. The MRI will be performed after the screening inclusion/exclusion criteria have been met. Assessments will be performed in the order noted on the time and events schedule:

- Obtain informed consent verified by signature on written informed consent
- Administer the MOCA
- Review demographics, medical/treatment history to determine eligibility based on inclusion/exclusion criteria
- Concomitant Medications and Treatments
- Perform vital sign check and EKG
- Draw blood for:
  - ApoE
  - Blood CBC, CMP, lipid panel, fibrinogen, CRP, LP-PLA2, MPOS, lipoprotein particles, Blood viscosity, B12, TSH
- Perform physical (including neurological) examination to determine eligibility based on inclusion/exclusion criteria
- Completion of “core clinical criteria” checklist(s) for the 2011 National Institute on Aging (NIA)-Alzheimer’s Association (AA) Guidelines on: (i) The diagnosis of dementia due to Alzheimer’s disease or (ii) The diagnosis of mild cognitive impairment due to Alzheimer’s disease
- Complete the Logical Memory I & II
- Administer the MMSE2
- Review inclusion/exclusion screening eligibility
- Perform MRI to rule out brain pathology, measure hippocampal volume and to assess exploratory endpoints (selected sites only). Brain pathology will include tumors, current or past bleeding, current or past aneurysms. The MRI should be done after the subject has been determined eligible to participate in the study. Initial screening MRI scan can be utilized if  $\leq 90$  days for subjects being re-screened.

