8.4.7 Week 12 – Day 84 (+/- 2 days)

- Cognitive assessments: It is recommended that subjects come in the day following treatment for all assessment testing but no later than 2 days (48 hours) post last treatment. Administer cognitive assessments including:
  - vADAS-Cog (must be administered first and before 3:00 PM; should be administered at the same time of day)
  - ADCS-CGIC
  - ADCS-ADL

---

Confidentiality Statement

---

The confidential information in this document is provided to you as an investigator or consultant for review by you, your staff, and the applicable Institutional Review Board. Your acceptance of this document constitutes agreement that you will not disclose the information contained herein to others without written authorization from the sponsor.

- Trail Making A & B
- Record vital signs (If non-treatment day)
- TUG Test
- Functional Reach Test
- Health Resource Utilization Survey - RUI
- NPI
- Exercise regimen
- Patient Questionnaire
- Review concomitant medications and treatments,
- Collect adverse events
- If treatment occurs on same day as assessments administer treatment first
  - Vitals (Pre & Post)
  - During the treatment phase, administer treatments 5 days per week but at a minimum 3 days per week up to a maximum of 35 treatments total (or during maintenance, administer two treatments per week separated by at least 2 days up to 24 weeks)
- Draw blood for:
  - Blood lipid panel, CBC, fibrinogen, CRP, LP-PLA2, MPO, lipoprotein particles to include: LDL-P, Lp(a)-P, VLDL-P, IDL-P, ApoB, B12, TSH
  - Blood viscosity

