8.4.14 Early Termination Visit

All procedures scheduled for the 12 month/final visit should be performed in the event of an early termination visit. The subject should be encouraged to complete these assessments.

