### 8.5.2 Laboratory Evaluations

Laboratory evaluations will occur at all the time points specified in the time and events schedule. The laboratory evaluations that will be performed are listed in **Figure 2**.

Blood Chemistry		
Sodium	Potassium	Blood urea nitrogen
AST	Glucose	Total bilirubin
ALT	Creatinine	Albumin
Total cholesterol	Serum calcium	Globulin
Triglycerides	Chloride	B12
Total protein	Bicarbonate	TSH
Hematology		
Hemoglobin	White blood cell count total and differential	
Hematocrit	Red blood cell count	
Platelets		
Exploratory Labs		
ApoE	CRP	Blood viscosity
Fibrinogen	LP-PLA2	
Lipid panel	MPOS	

Figure 2: Laboratory evaluations to be performed

Abnormal laboratory test results of a magnitude deemed clinically significant by the investigator will be repeated as soon as possible (preferably within 48 hours) to rule out laboratory error. For tests where there is a persistent abnormality, repeat analyses shall be performed until the cause is determined and return to baseline occurs or the investigator deems the abnormality to be of no clinical significance. If these values are deemed clinically significant then these tests should be discussed with the medical monitor. If these abnormalities are accompanied by clinical symptoms, then these should be captured as AEs.

---

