#### Confidentiality Statement

---

The confidential information in this document is provided to you as an investigator or consultant for review by you, your staff, and the applicable Institutional Review Board. Your acceptance of this document constitutes agreement that you will not disclose the information contained herein to others without written authorization from the sponsor.

A central laboratory will be used in this study. All details regarding the collection, shipment of samples, reporting of results and alerting extreme values will be provided by the central laboratory and compiled in a Laboratory Manual.

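### The itemised blood-draw lists for week 12, week 24 and month 12 omit the metabolic panel that other sections of the protocol repeat during the study

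*Protocol*

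**What the plan says.** Section 8.2 describes the CMP as a blood test of electrolytes, kidney and liver function and glucose. It adds: "Includes 14 blood tests that provide information about the current health status of the patient". The panel is done at baseline to check fitness for the study and is then "Performed at intervals during the study to confirm no change in" the subject's health.

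Section 8.5.2 states: "Laboratory evaluations will occur at all the time points specified in the time and events schedule". It refers to Figure 2 for the tests, and Figure 2 has a blood chemistry block. Table 2 marks Labs at screening, week 12, week 24 and month 12/early termination.

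The visit sections itemise the draws:

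- Screening (8.4.1), besides ApoE: "Blood CBC, CMP, lipid panel, fibrinogen, CRP, LP-PLA2, MPOS, lipoprotein particles, Blood viscosity, B12, TSH".
- Week 12 (8.4.7) opens with "Blood lipid panel, CBC, fibrinogen, CRP, LP-PLA2, MPO, lipoprotein particles to include" and goes on to named lipoprotein particles, ApoB, B12 and TSH, with blood viscosity as a separate item. Week 24 (8.4.11) and month 12 (8.4.13) carry the same list.
- Early termination (8.4.14): "All procedures scheduled for the 12 month/final visit should be performed in the event of an early termination visit".

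Section 5.2.2 includes safety "as reflected in adverse events, labs and vital signs" among the secondary endpoints, and section 9 lists laboratory parameters among the means of safety monitoring.

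**The concern.** Three places (8.2, 8.5.2 with Figure 2, and Table 2) point to chemistry being repeated after screening. The three lists that tell a site which tests to draw do not include it. The omission does not look like shorthand: the lists spell out individual lipoprotein particles and keep B12 and TSH, which 8.2 mentions in the CMP item, but not the CMP itself.

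At stake is the chemistry part of the laboratory safety data. If sites follow section 8.4, chemistry is measured at screening only, and the purpose that 8.2 gives for repeating it is not met. The procedure in 8.5.2 for repeating and discussing clinically significant abnormal results would then have no scheduled chemistry to act on after screening. Results not collected during the trial cannot be recovered later.

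**Working it through.** No sample size, power or error rate is involved. The check sets the passages side by side and counts.

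**1. CMP in the draw lists**

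| Visit | Labs marked in Table 2 | CMP named in the 8.4 list |
|---|---|---|
| Screening (8.4.1) | yes | yes |
| Week 12 (8.4.7) | yes | no |
| Week 24 (8.4.11) | yes | no |
| Month 12 (8.4.13) | yes | no |

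The CMP is in 1 of 4 lists, and in 0 of the 3 after screening. Early termination takes over the month-12 list, so it has the same gap.

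**2. What would be missing**

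Figure 2 lists 18 blood chemistry analytes. Four recur in the post-screening lists: total cholesterol and triglycerides (through the lipid panel), B12 and TSH. 18 − 4 = 14 have no scheduled draw after screening under 8.4: sodium, potassium, chloride, bicarbonate, blood urea nitrogen, creatinine, glucose, calcium, AST, ALT, total bilirubin, albumin, globulin and total protein. CBC also recurs.

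**3. Does another passage settle it?**

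Section 8.5.2, Table 2 and Figure 2 together place chemistry at week 12, week 24 and month 12, in line with 8.2. Figure 2 cannot be read as every test at every draw, because it also holds ApoE, which is listed for drawing at screening only. Section 8.2 says only that the repeats come at intervals. The chain supports 8.2 but does not remove the conflict with the lists.

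**4. Minor consistency points, all exploratory**

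- *Vascular measures.* Section 5.2.4 gives baseline, week 12 and week 24 for five measures: transcranial Doppler, flow-mediated dilation, pulse wave velocity, augmentation index and deep tissue oxygenation. Table 2 marks ultrasound/Moor at Day 1 and week 24 only, and 8.4.7 lists none. Section 5.1 speaks of Doppler or Moor at study start and repeatedly during the trial. The lists in 8.4.3 and 8.4.11 name transcranial Doppler, cerebral artery blood flow and Moor, but not flow-mediated dilation, pulse wave velocity or augmentation index; these appear only in a Table 2 footnote.
- *MRI.* Section 8.1 states a week-12 MRI. Section 5.1, Table 2 and 8.4.7 have none.
- *Digital-twin comparison.* Section 4 says 48 weeks and 5.2.4 says 12 months. Week 48 is 48 × 7 = Day 336. The month-12 visit is Day 365 ± 7, so the label is 365 − 336 = 29 days before the target and 358 − 336 = 22 days before the window opens. No visit is scheduled at Day 336.

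**The case against.** The strongest reply is that the protocol already requires the test: 8.5.2, Table 2 and Figure 2 put chemistry at named visits, and the 8.4 lists are merely loose. There is other evidence of looseness. Table 2 marks the MMSE2 at month 9, and the list in 8.4.12 omits it. This part stands. A reader might infer that no passage ties repeat chemistry to any visit, or that the visit lists rule it out. The documents support neither reading: the chain in 8.5.2 names the visits, and the lists omit the CMP without excluding it. What remains is a contradiction between that chain and the lists.

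A second reply is that sites will work from the laboratory manual. Section 8.5.2 says: "All details regarding the collection, shipment of samples, reporting of results and alerting extreme values will be provided by the central laboratory", compiled in that manual. It may well settle the matter, so the textual conflict is certain but the loss of data is not. A manual written from this protocol would still start from two conflicting sources.

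Third, 14 analytes without a later draw equals the 14 tests that 8.2 gives the CMP, and a reader might take this as proof that they are the same tests. It is not, because 8.2 never itemises them. The analytes fit its description, and the point does not depend on the match.

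Fourth, for the vascular measures one might conclude that week 12 should simply be struck from 5.2.4. That overlooks 5.1, which suggests interim measurement, and the visit lists, which do not name three of the five measures. The 48-week item is mostly a label: the protocol equates month 9 with week 36, and month 12 is the only visit that can supply the last value.

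**Conclusion.** The contradiction holds. Sections 8.2, 8.5.2 with Figure 2, and Table 2 indicate repeat chemistry at week 12, week 24 and month 12. The draw lists for those visits omit the CMP, and early termination inherits the omission. If sites follow the lists and the laboratory manual does not correct them, 14 of 18 Figure 2 chemistry analytes have no scheduled value after screening.

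A reader might infer that the laboratory part of the safety endpoint would be empty. It would not be: CBC, lipids, B12 and TSH recur, and section 5.1 allows a repeat lab draw at any time. No bias is claimed, and the primary endpoint and the randomised efficacy comparison are unaffected. The point should be fixed because safety data depend on it and the correction is cheap. The three minor points concern exploratory items only. Which passages reflect the intended schedule is for the sponsor to state.

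**What to change.** Reconcile the draw lists in 8.4.7, 8.4.11 and 8.4.13 (and, through 8.4.14, early termination) with 8.2, Table 2 and 8.5.2/Figure 2, so that the repeat CMP appears at the existing draws it is meant for. Check the laboratory manual against the result. This is a wording amendment: blood is already drawn at all three visits, so no visit or venipuncture is added.

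In the same amendment:

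- reconcile the week-12 vascular measures in 5.2.4 with 5.1, Table 2, 8.4.3, 8.4.7 and 8.4.11, and make clear at which visits flow-mediated dilation, pulse wave velocity and augmentation index are done;
- reconcile the week-12 MRI in 8.1 with 5.1, Table 2 and 8.4.7;
- align the 48-week label in section 4 with the 12-month visit in 5.2.4.

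These are text changes. Only a decision to keep a week-12 vascular measurement or a week-12 MRI would add procedures.

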### 8.3 Study Schedule

**Table 1: Renew™ NCP-5 Treatment Schedule**

Treatment Schedule	
Renew™ NCP-5 initial treatment visits	3-5 treatments per week to 35 treatments
Renew™ NCP-5 maintenance treatments	2 treatments per week as maintenance up to week 24

**Table 2: Renew™ NCP-5 Visit Schedule**

Evaluation/ Procedure	Screening	Baseline	Randomization / T1	Weeks 1-6	Week 6 Assessment	Weeks 7-12	Week 12 Assessment	Weeks 13-18	Week 18 Assessment	Week 19-24	Week 24 Assessment	9 Month Assessment	12 Month / Early Termination
Procedure Window by Study Day or Treatment Day	Day -35 to Day -7	Day -14 to Day -1	Day 1		Day 42 (+/- 2 Days)		Day 84 (+/- 2 Days)		Day 126 (+/- 2 Days)		Day 168 (+/- 2 Days)	Day 252 (+/- 7 Days)	Day 365 (+/- 7 Days)
Informed Consent	X												
MOCA	X										X	X	X
Demographics	X												
Medical, Treatment & Procedure History	X											X*****	
Vitals**	X	X	X	X	X	X	X	X	X	X	X	X	X
EKG	X												
Labs	X						X				X		X
Physical Exam (including Neuro)	X												X
Hachinski Scale Assessment		X									X	X	X
2011 NIA Checklist Administration (MCI or AD checklist to be administered)	X												
CVR Calculation		X											
Exercise Regimen		X			X		X		X		X	X	X
TUG Test		X			X		X		X		X	X	X

---

**Confidentiality Statement**

---

The confidential information in this document is provided to you as an investigator or consultant for review by you, your staff, and the applicable Institutional Review Board. Your acceptance of this document constitutes agreement that you will not disclose the information contained herein to others without written authorization from the sponsor.

Evaluation/ Procedure	Screening	Baseline	Randomization / T1	Weeks 1-6	Week 6 Assessment	Weeks 7-12	Week 12 Assessment	Weeks 13-18	Week 18 Assessment	Week 19-24	Week 24 Assessment	9 Month Assessment	12 Month / Early Termination
Procedure Window by Study Day or Treatment Day	(Day -35 to Day -7)	Day -14 to Day -1	Day 1		Day 42 (+/- 2 Days)		Day 84 (+/- 2 Days)		Day 126 (+/- 2 Days)		Day 168 (+/- 2 Days)	Day 252 (+/- 7 Days)	Day 365 (+/- 7 Days)
Functional Reach Test		X			X		X		X		X	X	X
Patient Questionnaire		X			X		X		X		X	X	X
vADAS-Cog****		X			X		X		X		X	X	X
ADCS-CGIC****		X			X		X		X		X	X	X
ADCS-ADL****		X			X		X		X		X	X	X
Trail Making Test A & B ****		X			X		X		X		X	X	X
Logical Memory I & II****	X										X	X	X
MMSE2	X										X	X	X
NPI		X			X		X		X		X	X	X
Health Resource Utilization Survey (RUI)		X					X				X	X	X
Patient Satisfaction Survey													X
Inclusion and Exclusion Eligibility Checks	X	X	X										
Randomization			X										
NCP-5 Treatment			X	X		X		X		X			
MRI (including hippocampal volume)***	X										X*****		X*****
Ultrasound/MOOR deep tissue oxygenation***			X								X		
AE		X	X	X	X	X	X	X	X	X	X	X	X
Concomitant Medications	X	X	X	X	X	X	X	X	X	X	X	X	X
Con-Treatments	X	X	X	X	X	X	X	X	X	X	X	X	X
Study Disposition													X

\*Day 1 = first treatment day. All visit windows are based on the 1st treatment date

\*\*Vitals are pre & post treatment except for screening and Month 12/ET

\*\*\*The initial MRI will be performed after the participant meets the initial screening criteria. Only designated sites will perform MRI to assess regional CBF, regional brain volume, resting state connectivity and/or Ultrasound to assess Flow Mediated dilation, pulse wave velocity, AI, Transcranial Doppler, Cerebral artery blood flow, Moor deep tissue oxygenation.

\*\*\*\*vADAS-Cog assessment **MUST** be the first cognitive test administered, and all cognitive assessments **MUST** be completed before labs and imaging. Cognitive tests can be administered on the same day as treatment visit but must be done before 3:00 PM and **after** treatment is completed.

\*\*\*\*\* MRI must be done after last treatment but may take place on or before the Week 24 assessment visit

\*\*\*\*\*MRI must be completed within 14 Days prior to the Month 12 Visit

\*\*\*\*\*If not collected at screening visit

## 8.4 Study Visits

### 8.4.1 Screening (-35 to -7 days prior to baseline)

Screening assessments ascertain whether the patient is eligible to participate in the study. Assessments that require the least imposition on the patient and the staff will be performed first to exclude patients before they are subjected to more demanding assessments. As necessary, screening may be performed on multiple visits. The MRI will be performed after the screening inclusion/exclusion criteria have been met. Assessments will be performed in the order noted on the time and events schedule:

- Obtain informed consent verified by signature on written informed consent
- Administer the MOCA
- Review demographics, medical/treatment history to determine eligibility based on inclusion/exclusion criteria
- Concomitant Medications and Treatments
- Perform vital sign check and EKG
- Draw blood for:
  - ApoE
  - Blood CBC, CMP, lipid panel, fibrinogen, CRP, LP-PLA2, MPOS, lipoprotein particles, Blood viscosity, B12, TSH
- Perform physical (including neurological) examination to determine eligibility based on inclusion/exclusion criteria
- Completion of “core clinical criteria” checklist(s) for the 2011 National Institute on Aging (NIA)-Alzheimer’s Association (AA) Guidelines on: (i) The diagnosis of dementia due to Alzheimer’s disease or (ii) The diagnosis of mild cognitive impairment due to Alzheimer’s disease
- Complete the Logical Memory I & II
- Administer the MMSE2
- Review inclusion/exclusion screening eligibility
- Perform MRI to rule out brain pathology, measure hippocampal volume and to assess exploratory endpoints (selected sites only). Brain pathology will include tumors, current or past bleeding, current or past aneurysms. The MRI should be done after the subject has been determined eligible to participate in the study. Initial screening MRI scan can be utilized if  $\leq 90$  days for subjects being re-screened.

### 8.4.2 Baseline Visit (Day -14 – Day -1)

- Vital Signs
- Administer Hachinski
- CVR calculation
- Review exercise regimen
- Patient questionnaire
- Administer baseline cognitive assessments including:

---

#### Confidentiality Statement

---

The confidential information in this document is provided to you as an investigator or consultant for review by you, your staff, and the applicable Institutional Review Board. Your acceptance of this document constitutes agreement that you will not disclose the information contained herein to others without written authorization from the sponsor.

- vADAS-Cog (must always be administered first and before 3:00 PM)
- ADCS-CGIC for clinician and patient/caregiver
- ADCS-ADL
- Trail Making A&B
- TUG Test
- Functional Reach Test
- Health Resource Utilization Survey - RUI
- NPI
- Review concomitant medication and treatments
- Collect adverse events
- Schedule study visits for eligible subjects
- Verify inclusion/exclusion criteria

#### 8.4.3 Randomization/First Treatment Day (Day 1)

Randomization must occur after eligibility confirmation and prior to first treatment. The following assessments should be performed during this visit:

- Verify inclusion/exclusion criteria
- Randomize subject
- Review concomitant medications and treatments
- Collect adverse events
- Record vital signs (Pre & Post)
- Administer treatment (All treatment subjects will have an initial four treatments (which are part of the planned 35 treatments) in which the PSI will be gradually increased to maximum tolerability with the goal of reaching 3-6 PSI by the fifth treatment).

For sites collecting data for exploratory endpoints, complete the following assessments:

- Ultrasound: Transcranial Doppler; cerebral artery blood flow
- Moor deep tissue oxygenation (selected sites only)

